6 STATISTICAL CONSIDERATIONS

6.1 Primary Endpoint

The primary aim of this study is to determine if pancreatic enzymes improve enteral fat absorption in subjects with SBS. Enteral fat absorption will be measured as CFA. For each subject, CFA will be compared before and after administration of pancreatic enzyme medication.

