Safety Evaluations	Safety will be monitored by adverse events reporting. The frequencies of AEs by type, body system, severity and relationship to study supplement will be summarized. SAEs (if any) will be described in detail.
Statistical And Analytic Plan	
The goal of the primary aim of the study is to compare the outcome CFA before and after pancreatic enzyme medication administration in subjects with SBS. The secondary outcomes of CNA and BC will also be compared in subjects with SBS before and after pancreatic enzyme medication administration. Descriptive statistics for CFA, CNA, and BC outcomes (mean, standard deviation, median, range, 95% CI) will be calculated for the SBS cohort before and after pancreatic enzyme medication administration with paired t-tests or Wilcoxon sign rank tests depending on skewness of data.
 
For the MBT outcomes, a moment-based pharmacokinetic (PK) analysis will be performed based on non-compartmental methodology using WinNonLin version 9.1 (Pharsight, Cary, NC). Baseline (C_0) and maximum (C_{max}) plasma concentrations are calculated, and area under the curve from time zero to eight hours (AUC) is calculated using the linear trapezoid method. PK parameters can then be compared between treatment groups using a paired t-test or Wilcoxon signed rank test as appropriate. To describe HA exposure relative to that of PA, the ratio of the HA to PA C_{max} (C_{max} HA/PA) and AUC (AUC HA/PA) is calculated for each subject after molar transformation and dose-normalization of exposure metrics⁷. Alternately, population PK analyses for repeated-measures endpoints can be conducted via nonlinear mixed-effects modeling with a qualified installation of the nonlinear mixed-effects modeling (NONMEM) software, Version VII, Level 2.0 (ICON Development Solutions, Hanover, MD⁸. Using this method, population PK modeling is conducted by simultaneously fitting structural PK models to both PA and HA concentrations⁹.
 
Descriptive statistics (mean, standard deviation, median, range, 95% CI) will also be employed to assess outcomes related to intestinal hormone signaling that controls pancreatic enzyme secretion and intestinal adaptation in H4 (glucagon-like peptide 2, insulin-like growth factor 1, insulin-like growth factor binding protein 3, and growth hormone concentrations). All variables will be tested for normality and nonparametric tests used as appropriate. The change in status for these variables before and after pancreatic enzyme medication administration will be explored with paired t-tests and Wilcoxon sign rank tests depending on skewness.

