Pancreatic enzymes have been successful in improving enteral absorption in several patient populations, most notably in cystic fibrosis^{4,5}. The impact of pancreatic enzymes on enteral absorption has not been evaluated in patients with SBS and will be the main focus of this study.

Our primary objective is to demonstrate that treating patients with SBS with pancreatic enzymes will improve enteral fat absorption. However, exploratory aspects of the study also address the changes that nutrient absorption will have on intestinal adaptation and enteroendocrine hormone signaling.

SBS is a life threatening disease process with a paucity of noninvasive therapies that directly improve enteral absorption and improve patient outcome. Maximizing absorption to reduce parenteral nutrition needs in this patient population will be essential in reducing morbidity and mortality. This study will also provide further information on the mechanisms of malabsorption in patients with SBS, which could facilitate identification of other therapeutic targets to improve enteral absorption. It will provide the framework for larger studies to improve enteral absorption in patients with SBS.

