1.4 Selection of Drugs and Dosages

This is a proof of concept study and the use of pancreatic enzymes in short bowel syndrome has not been studied before. As a result, our preference would be to use the highest doses of pancreatic enzyme that are deemed safe for our subjects in order to assess if absorption can be improved.

We have based pancreatic enzyme dosing on typical dosing used by the senior dietitian and a senior physician at the Cystic Fibrosis Center at the Children's Hospital of Philadelphia (CHOP) and as recommended by the most recent consensus statement on pancreatic enzyme dosing in cystic fibrosis¹². The recommended dosing for meals ranges from 500 – 2500 lipase units/kg/meal. The CF Center at CHOP uses a maximum dose of 2500 lipase units/kg/meal and 1250 lipase units/kg/snack. We will aim to administer about 1500 – 2500 lipase units/kg/meal and 750 – 1250 lipase units/kg/snack in this study (see Table 5 below). Exact dosing will depend on the subject's complicated enteral feeding regimen. Pancreatic enzyme dosing will be weight based and we will not exceed 10,000 lipase units/kg/day for each patient^{12,13}.

We anticipate that several subjects in this study will have a complicated enteral feeding regimen that may be comprised of one or more of the following options: 1) bolus gastrostomy tube feeds, 2)

continuous overnight gastrostomy tube feeds, and 3) continuous gastrostomy tube feeds for 18 -24 hours of the day. Please see Table 5 below for a summary of goal pancreatic enzyme dosing for each of these enteral feeding regimens. Subjects should be able to take pancreatic enzyme medication orally in order to be included in the study even if they rely on a gastrostomy tube or jejunostomy tube.

Table 5. Goal Pancreatic Enzyme Dosing*

	Pancreatic Enzyme Dosing
Meal	1,500 – 2,500 lipase units/kg/meal
Snack	750 – 1,250 lipase units/kg/snack
Bolus enteral feeds (typically 1 hour infusion)	1,500 – 2,500 lipase units/kg/meal administered with each bolus ⁺
Overnight enteral feeds (typically 8-12 hours)	1,500 – 2,500 lipase units/kg/meal administered at the start and end of the feed
Continuous enteral feeds (typically 20-24 hours)	
 • 1,500 – 2,500 lipase units/kg/meal administered at the start and end of the feed • While awake and during continuous feed, enzymes dosed every 4 hours based on grams of fat in formula (not to exceed 4,000 lipase units/grams of fat/day)

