3.2 Allocation to Treatment Groups and Blinding

This is an open-label intervention therapeutic exploratory study, and not a randomized controlled trial.

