4.2 Study Treatment Phase

Subjects will have 2-4 visits in this study that will all occur at The Children's Hospital of Philadelphia. Study visit 0 will be to obtain informed consent and laboratories may be drawn (see description below). Study Visit #1 will be without pancreatic enzyme medication and Study Visit #2 will occur after they receive Creon™ as their pancreatic enzyme medication therapy. Study visit #3 will be off of study doses of pancreatic enzyme medication, though subjects on pancreatic enzymes at baseline may resume their regular dose. Study visit #3 will be to assess subject well-being, medication adherence, and to drop off stool collected and dietary records.

Study Visit #1 includes anthropometrics and baseline laboratories. A spot stool sample will be collected to determine stool pH. Subjects in the MBT/CCK cohort will have the MBT performed as well and a serum CCK concentration as part of their laboratories. Study Visit #2 includes repeat laboratories, which will not include micronutrient levels. A spot stool sample will be collected to determine stool pH. Subjects in the MBT/CCK cohort will again have the MBT performed and a serum CCK concentration drawn. (refer to study procedures in Table 1).

Study Visit 0: Visit for Consent and HIPAA Authorization for release of medical record information

- Informed Consent will be obtained at study visit 0. Subjects will have the option to complete this study visit via telephone. If subjects are taking pancreatic enzyme medication and will need to discontinue medication 3 days prior to Study Visit #1, a signed, informed consent form will be obtained in person or by mail, fax, or email prior to the beginning of any discontinuation of the medication. If subjects are taking a medication that directly alters fat absorption and will need to discontinue medication one week prior to Study Visit #1, a signed, informed consent form will be obtained prior to the beginning of any discontinuation of the medication. Medications that alter fat absorption will not be discontinued without the permission of the primary gastroenterologist. We will obtain a signed, informed consent form for all subjects in the MBT/CCK cohort prior to initiation of fasting or dietary changes for study visit 1. HIPAA Authorization forms from the subjects' institutions will be obtained and will be signed in person or obtained by mail/fax/email.

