6.3.1 Efficacy Analysis

Statistical Analysis: **H1, H2, and H3:** Descriptive statistics for CFA, CNA, and BC outcomes (mean, standard deviation, median, range, 95% CI) will be calculated for the SBS cohort before and after PERT administration with paired t-tests or Wilcoxon sign rank tests depending on skewness of data. For the MBT outcomes, a moment-based pharmacokinetic (PK) analysis will be performed based on non-compartmental methodology using WinNonLin version 9.1 (Pharsight, Cary, NC). Baseline (C_0) and maximum (C_{max}) plasma concentrations are calculated, and area under the curve from time zero to eight hours (AUC) is calculated using the linear trapezoid method. PK parameters can then be compared between treatment groups using a paired t-test or Wilcoxon signed rank test as appropriate. To describe HA exposure relative to that of PA, the ratio of the HA to PA C_{max} (C_{max} HA/PA) and AUC (AUC HA/PA) is calculated for each subject after molar transformation and dose-normalization of exposure metrics⁷. Alternately, population PK analyses for repeated-measures endpoints can be conducted via nonlinear mixed-effects modeling with a qualified installation of the nonlinear mixed-effects modeling (NONMEM) software, Version VII, Level 2.0 (ICON

Development Solutions, Hanover, MD⁸. Using this method, population PK modeling is conducted by simultaneously fitting structural PK models to both PA and HA concentrations⁹.

In exploratory analyses, we will compare the estimates of percent fat absorption from the MBT with both the CFA% from the 72-hour fecal fat and diet analysis and the BC results (energy loss in the stool). We will compare the methods for detection of fat malabsorption as measured by CFA% and BC with fat absorption as measured by MBT for the subjects before and after pancreatic enzyme medication use. A correlation analysis will be conducted to evaluate the performance of the MBT relative to that of the CFA%. HA and PA C_{max}, AUC, and HA/PA ratios will be plotted against CFA% or BC caloric loss to explore the relationship between the two tests. Any relationships observed in the plots will be further explored using correlation analysis and appropriate regression analysis as dictated by the observations.

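### Does the fixed-order, single-arm CFA comparison need a written limit on its causal reading and one HA/PA ratio named to support it?

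*Combined protocol and SAP*

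**What the plan says.** The aim is worded causally in 6.1 ("The primary aim of this study is to determine if pancreatic enzymes improve enteral fat absorption in subjects with SBS") and 2.1. Section 1.1 is stronger still: "Our primary objective is to demonstrate that treating patients with SBS with pancreatic enzymes will improve enteral fat absorption", and 1.5 repeats it.

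The order of conditions is the same for everyone. Section 4.2 has "Study Visit #1 will be without pancreatic enzyme medication and Study Visit #2 will occur after they receive" Creon. Section 6.3.1 analyses CFA "with paired t-tests or Wilcoxon sign rank tests depending on skewness of data". The synopsis gives the goal of the primary aim as "to compare the outcome CFA before and after pancreatic enzyme medication administration in subjects with SBS", and the last sentence of 6.1 defines the comparison the same way, within each subject.

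The nature of the study is stated plainly. Section 3.2: "This is an open-label intervention therapeutic exploratory study, and not a randomized controlled trial"; 9.1 says the same. Section 1.4: "This is a proof of concept study and the use of pancreatic enzymes in short bowel syndrome has not been studied before"; 7.1.3 repeats it. The synopsis rationale and 1.1 present the study as groundwork for larger ones.

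For the malabsorption blood test (MBT), 5.2.2 lists the within-subject change in the HA/PA ratio among its outcomes. Section 6.3.1 derives a Cmax ratio and an AUC ratio, provides for paired tests of the PK parameters, and adds a comparison of methods: "A correlation analysis will be conducted to evaluate the performance of the MBT relative to that of the CFA". Section 6.4 calls the MBT exploratory, in a subset of 10.

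**The concern.** A significant paired test shows that mean CFA differed between two periods. The aim asks whether enzymes caused the difference. With fixed order and no control, a period effect cannot be separated from a treatment effect, and such effects are possible here:

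- Diet is the subject's own in both periods and is recorded at home, and recorded fat intake is the denominator of CFA (5.2.2).
- Drugs that alter fat absorption stop seven days before Visit 1 and stay stopped (4.3), so time off them differs between the two collections.
- Subjects whose parenteral nutrition changes for more than three days may remain in the study (4.6).

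The plan's own cited randomised trial shows CFA rising on placebo (6.4). The synopsis rationale expects a positive finding to increase clinical use of enzymes in SBS, so over-reading would matter.

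The MBT seems to offer help. Its meal is fixed, and 1.5 explains that free fatty acid absorption does not need lipase, so HA relative to PA should respond to enzymes specifically. Yet the plan does not name one of the two ratios as the one to rely on, and does not tie either to interpretation of the CFA result. The remedy that suggests itself is a sentence limiting the conclusion, plus one ratio named in advance as supportive evidence.

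**Working it through.** **1. The plan's power figure.** Inputs from 6.4: n = 22, difference 9 points, SD of differences 14, two-sided 0.05, paired t-test. The noncentral t with 21 df and noncentrality (9/14)·√22 gives 82.0%, against the stated 80%. The figure reproduces; n = 21 already gives 80.0%.

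**2. Smallest significant change.** t(0.975, 21)·SD/√22 over the SD range in 6.4:

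| SD | Smallest significant mean change |
|---|---|
| 12 | 5.3 |
| 14 | 6.2 |
| 18 | 8.0 |

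**3. The cited placebo-controlled trial (6.4).** On enzymes: 86.1 − 66.5 = 19.6. On placebo: 72.9 − 67.0 = 5.9. Difference: 19.6 − 5.9 = 13.7, as the plan states. The placebo change is 5.9/19.6 = 30% of the change on enzymes. The patients had chronic pancreatitis.

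**4. Inert drug with a drift between periods.** Probability of p<0.05 at n = 22, by the noncentral t. The SDs are the plan's SDs of change on enzymes; applying them to an inert drug is an assumption, and so is each drift.

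| Drift (points) | SD 12 | SD 14 | SD 18 |
|---|---|---|---|
| 0 | 5.0% | 5.0% | 5.0% |
| 1 | 6.6% | 6.2% | 5.7% |
| 3 | 20.1% | 16.0% | 11.6% |
| 5.9 | 59.5% | 47.1% | 31.1% |

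**5. At the target result.** 9 ± 6.2 gives a 95% CI of 2.8 to 15.2. A drift of 2.8 would bring the lower limit to zero but leave 9 − 2.8 = 6.2 points, so it would not explain the change by itself.

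**6. What HA/PA could add.** Inputs from 6.4: difference about 0.5, SD about 0.7, taken here as the SD of paired change (the plan does not say). The half-width is t(0.975, n−1)·0.7/√n.

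| n | Half-width | Expected 95% CI | Power |
|---|---|---|---|
| 10 | 0.50 | 0.0 to 1.0 | 52% |
| 8 | 0.59 | −0.1 to 1.1 | 41% |

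Power of 80% would need 18 subjects. Testing both ratios at 0.05 raises the false-positive chance to 9.8% if they are independent, and to about 8.0% or 7.3% at correlations of 0.8 or 0.9.

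**7. What the remedy would change.** With the limiting sentence added, the test, the estimate and the interval stay as they are. With one ratio named, its paired comparison is the one that 5.2.2 and 6.3.1 already provide for, in the same adults and the same fixed order.

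**The case for a change.** The strongest case for a change is that disclosing a design is not the same as stating what its result may conclude. The aim says improve, two sections say demonstrate, and nothing in section 6 holds a positive result to a before-to-after change. A sentence costs nothing. Naming one ratio before the data are seen would stop anyone choosing whichever agrees with CFA.

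Part of this stands. No sentence states the limit, and the confounding is real. If HA/PA were later cited in support of the CFA result, the choice of ratio should have been made before any MBT data were viewed.

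The rest does not carry a change:

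- The test is valid for its null of no mean change, and the plan defines the comparison as before versus after.
- The largest probability rests on a placebo change from another disease; at the planned SD, an observed change of 5.9 would itself miss significance.
- Several features restrain drift: stable health for two weeks and no medication changes at entry, about two weeks between visits, laboratory measurement of stool fat, and no CFA threshold at entry, which limits regression to the mean.
- HA/PA is measured in the same order, in at most 10 adults who may decline and in none of the 16 children. Neither a positive nor a null result would settle attribution, so making it formal support for the primary result would invite over-reading.

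**Conclusion.** No change to the plan is needed. The gap between causal wording and an uncontrolled, fixed-order comparison is real. However, the design is disclosed throughout, and an analyst will report the result as a before-to-after change in CFA with its interval and discuss period effects as a limitation. An added caveat would leave every number unchanged.

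The size of the problem in SBS is unknown. Under the stated assumptions (n = 22, SD 14, inert drug), the chance of p<0.05 runs from 6% at a 1-point drift to 47% at 5.9 points, and the upper figure is borrowed from chronic pancreatitis. An accepted weakness of an exploratory single-arm study is a fair trade-off when larger studies are meant to follow.

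On HA/PA, the paired comparison is already planned and rightly kept exploratory. With about 52% power at n = 10, assuming that 0.7 is a paired SD, naming one ratio would gain little.

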6.2 Secondary Endpoint

The **secondary aim** of this proposal is to assess the effect that administration of pancreatic enzymes will have on global absorption. Specifically, CNA and stool BC will be measured to detect changes in enteral protein absorption and stool energy losses, respectively, before and after administration of pancreatic enzymes.

An additional **secondary aim** includes that we will **explore** the ability of the MBT to detect changes in enteral fat absorption before and after administration of pancreatic enzymes in a subset of patients. This test will also help characterize the degree of pancreatic insufficiency in subjects.

A final **secondary aim** will **explore** if improved lipid digestion and release of free fatty acids due to pancreatic enzymes will promote intestinal adaptation by stimulating endocrine signaling. Specifically, GLP-2, IGF-1, IGFBP-3, and GH concentrations will be measured from blood samples before and after administration of pancreatic enzymes. CCK will also be measured in the MBT/CCK Cohort only before and after administration of pancreatic enzymes. Plasma citrulline will also be measured as a marker of intestinal adaptation before and after administration of pancreatic enzymes.

6.3 Statistical Methods

Analysis will begin with descriptive analyses of the study sample using means, standard deviations, medians, and ranges for continuous variables, and frequency distributions for categorical variables. Descriptive statistics and exploratory graphing such as frequencies, means, standard deviations, box plots, and scatter plots will be used to assess the normality of the data in terms of the presence of skew and/or outliers.

6.3.1 Efficacy Analysis

Statistical Analysis: **H1, H2, and H3:** Descriptive statistics for CFA, CNA, and BC outcomes (mean, standard deviation, median, range, 95% CI) will be calculated for the SBS cohort before and after PERT administration with paired t-tests or Wilcoxon sign rank tests depending on skewness of data. For the MBT outcomes, a moment-based pharmacokinetic (PK) analysis will be performed based on non-compartmental methodology using WinNonLin version 9.1 (Pharsight, Cary, NC). Baseline (C_0) and maximum (C_{max}) plasma concentrations are calculated, and area under the curve from time zero to eight hours (AUC) is calculated using the linear trapezoid method. PK parameters can then be compared between treatment groups using a paired t-test or Wilcoxon signed rank test as appropriate. To describe HA exposure relative to that of PA, the ratio of the HA to PA C_{max} (C_{max} HA/PA) and AUC (AUC HA/PA) is calculated for each subject after molar transformation and dose-normalization of exposure metrics⁷. Alternately, population PK analyses for repeated-measures endpoints can be conducted via nonlinear mixed-effects modeling with a qualified installation of the nonlinear mixed-effects modeling (NONMEM) software, Version VII, Level 2.0 (ICON

Development Solutions, Hanover, MD⁸. Using this method, population PK modeling is conducted by simultaneously fitting structural PK models to both PA and HA concentrations⁹.

In exploratory analyses, we will compare the estimates of percent fat absorption from the MBT with both the CFA% from the 72-hour fecal fat and diet analysis and the BC results (energy loss in the stool). We will compare the methods for detection of fat malabsorption as measured by CFA% and BC with fat absorption as measured by MBT for the subjects before and after pancreatic enzyme medication use. A correlation analysis will be conducted to evaluate the performance of the MBT relative to that of the CFA%. HA and PA C_{max}, AUC, and HA/PA ratios will be plotted against CFA% or BC caloric loss to explore the relationship between the two tests. Any relationships observed in the plots will be further explored using correlation analysis and appropriate regression analysis as dictated by the observations.

Descriptive statistics (mean, standard deviation, median, range, 95% CI) will also be employed to assess outcomes related to intestinal hormone signaling that controls pancreatic enzyme secretion and intestinal adaptation in **H4** (glucagon-like peptide 2, insulin-like growth factor 1, insulin-like growth factor binding protein 3, and growth hormone concentrations). All variables will be tested for normality and nonparametric tests used as appropriate. The change in status for these variables before and after PERT administration will be explored with paired t-tests and Wilcoxon sign rank tests depending on skewness.

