1 BACKGROUND INFORMATION AND RATIONALE

1.1 Introduction

Short bowel syndrome (SBS) occurs when there is a history of prior bowel resection and the residual functional intestinal mass is insufficient to allow for adequate absorption of fluid, electrolytes, nutrients, and micronutrients provided by an age appropriate diet. There are several etiologies of SBS, which differ between pediatric and adult populations. In adults, the most common causes of SBS include mesenteric ischemia, Crohn disease, malignancy, radiation enteritis, surgical complications, and trauma⁶. In pediatric patients, SBS is most commonly due to necrotizing enterocolitis and congenital anomalies, such as intestinal atresia, gastroschisis, and malrotation¹⁰.

Patients with SBS have a high mortality rate that is mainly attributed to complications from central venous access and parenteral nutrition¹. In 2012, Squires et al¹ published the largest retrospective review to date that described outcomes for patients with SBS at fourteen centers in the United States. The study showed that over a 5-year period, the mortality rate was 27%. Central venous access and parenteral nutrition also expose patients to an increased risk of several morbidities, including gallstones, cholestatic liver disease, glucose instability, deep vein thromboses, bone disease, and emboli. The ultimate goal in clinical management of patients with SBS is to wean off of parenteral nutrition and establish enteral autonomy. This goal can be difficult to achieve due to the significant malabsorption that occurs in SBS. Madsen et al² studied a cohort of subjects with short bowel syndrome, high stool output, and high fecal energy losses and demonstrated that they had a low coefficient of fat absorption of about 48%. This study demonstrates how significant malabsorption can be in patients with SBS and therefore highlights the challenge that clinicians face in attempting to minimize parenteral nutrition use.

There are few medical therapies that improve absorption in patients with SBS. To date, teduglutide, a glucagon-like-peptide 2 (GLP-2) analog, is the only medication that has been clinically shown to improve intestinal adaptation and allow parenteral nutrition to be weaned in adults³. This drug shows great promise, but there are several concerns, such as increased risk of cancer and a loss of response with drug withdrawal.

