3.3.2 Total Number of Study Sites/Total Number of Subjects Projected

The study will be conducted at two investigative site in the United States, the Children's Hospital of Philadelphia and the University of Pennsylvania. Recruitment will occur across regional centers as described above. All study visits will occur at The Children's Hospital of Philadelphia.

Recruitment will stop when 16 subjects with SBS between the ages of 4 and 17.9 years are enrolled and when 10 subjects with SBS between the ages of 18 years and 75 years are enrolled. It is expected that 26 subjects will be enrolled to produce at least 22 evaluable subjects.

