3.4 Study Population

3.4.1 Inclusion Criteria

General Inclusion Criteria for all Subjects

- History of a prior small bowel resection
 - If small bowel resection occurred under 18 years of age, subjects must have dependence on parenteral nutrition for at least three months following small bowel resection
 - If small bowel resection occurred at 18 years of age or older, subjects must have 200 centimeters or less of residual bowel length and must have more than 3 bowel movements per day following small bowel resection
- Age 4 years to 75 years
- Usual state of health for the past two weeks with no medication changes
- Able to participate in a study for about four weeks with four study visits
- Able to take pancreatic enzyme medication orally

MBT/CCK Subset Inclusion Criteria

- Age 18 years to 75 years

All available details of estimated bowel length will be taken into account, but there are no inclusion restrictions based on this information.

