6.4 Sample Size and Power

Sample Size Considerations: The primary hypothesis (**H1**) of this study is: 1) the CFA will detect changes in fat absorption with PERT administration in subjects with SBS. The sample size selected for the SBS cohort (n=26) is based upon our previous experience in cystic fibrosis (CF) and chronic pancreatitis (CP) in detecting changes over time before and after administration of PERT. Although few studies of fecal fat loss in subjects with SBS have been conducted, losses of about 48% of fat intake in the stool have been reported². For the CFA outcome, our experience has been in CF and pancreatic insufficiency (PI), with average CFA of 81±14% in one study³⁰ and 83±10% in another³¹ when subjects were on PERT. In comparison, healthy subjects have CFA ≥93%. From the literature for CP, a number of clinical trials have used CFA to describe fat malabsorption in subjects with CP and confirmed PI before and after administration of PERT. Ramesh et al³² found an increase in CFA from 66.7±14.0% before PERT to 88.9±5.2% after PERT (change of 22.7±12.2%) in adults with CP from India. Thorat et al³³, in a randomized controlled trial in India, saw CFA increase from 66.5±14.1 to 86.1±7.5% in those taking PERT compared to an increase from 67.0±14.0 to 72.9±11.5% for placebo, a treatment effect of 13.7% (95% CI: 9.1, 18.2) after 1 week of PERT. Drawing from the literature on CP in the absence of information for SBS, the change in CFA for subjects with CP and confirmed PI before and after PERT administration has ranged from 8 to 23% with the SD of that change ranging from 12 to 18%, but averaging at 14%. 22 subjects will have 80% power to detect a difference in means of 9% (increase in CFA% from 85 to 94% after PERT administration), assuming a SD of differences of 14%, using a paired t-test with $\alpha = 0.05$ two-sided significance level.

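### Children and adults are recruited to separate fixed quotas, but the change in CFA is tested as one unstratified cohort, which makes the test conservative and costs power if the two groups respond differently

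*Combined protocol and SAP*

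**What the plan says.** Section 3.3.2 sets the age mix by quota. "Recruitment will stop when 16 subjects with SBS between the ages of 4 and 17.9 years are enrolled", and the same sentence closes adult recruitment (18 to 75 years) at 10. It expects 26 enrolled to give at least 22 evaluable.

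Section 6.3.1 treats these subjects as a single sample. Descriptive statistics for CFA, CNA and BC, including a 95% CI, "will be calculated for the SBS cohort before and after PERT administration with paired t-tests" or Wilcoxon tests, depending on skewness. The interval is attached to the values before and after treatment; none is stated for the change itself.

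Section 6.4 powers the study in the same way: "22 subjects will have 80% power to detect a difference in means of 9" CFA points, "assuming a SD of differences of 14" points, "using a paired t-test with $\alpha = 0.05$ two-sided significance level". No section plans stratification by age group, an estimate by age group or a check of response by age.

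The background in section 1.1 treats the two populations as different in origin: "There are several etiologies of SBS, which differ between pediatric and adult populations".

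**The concern.** A paired t-test on the whole cohort estimates its standard error from the spread of all individual changes around one common mean. If children and adults have different mean changes, part of that spread is the gap between the groups. Had the age mix been left to chance, the gap would be a real source of sampling variation. Here the quotas fix the mix, so repeated trials would not vary in that respect, and the pooled standard error is too large for the mean change at that mix.

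Two things are at stake. One is power, in a study sized close to 80%. The other is what the result shows: the primary hypothesis speaks of subjects with SBS from 4 to 75 years, and nothing pre-specified would let a reader see whether both age groups contributed to the mean.

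**Working it through.** **The plan's own figure.** Paired t-test, n = 22, mean change 9, SD of differences 14, two-sided 0.05 (section 6.4). Noncentrality = 9 / (14/√22) = 3.02 on 21 df, giving power of 82.0%. The smallest n for 80% is 21. The stated 80% therefore reproduces.

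**Inputs.**
- Quotas of 16 and 10, and 22 evaluable: section 3.3.2.
- Overall SD of change 14: section 6.4.
- Evaluable split of 14 children and 8 adults: assumption, close to the quota ratio.
- Child-adult difference in mean change, D: assumption, since the documents give none. Values of 0, 5, 10 and 15 points are shown. For scale, section 6.4 says the change in chronic pancreatitis studies "has ranged from 8 to 23% with the SD of that change ranging from 12 to 18%, but averaging at 14" points, but that is spread between studies, not between age groups.

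**Formulas.** With p = 14/22, the between-group part of the variance is p(1 − p)D² = 0.2314 D². Holding overall variance at 14² = 196, the within-group SD is σw = √(196 − 0.2314 D²).
- Pooled analysis: half-width t(21) × 14/√22 = 2.080 × 2.985 = 6.2.
- Stratified analysis (change regressed on a centred age-group indicator): the same point estimate, half-width t(20) × σw/√22.

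Example at D = 10: 0.2314 × 100 = 23.1; σw = √172.9 = 13.15; half-width 2.086 × 13.15/4.690 = 5.8.

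**Results.** Power for a mean change of 9 and coverage are from simulation with the age mix fixed (100,000 runs).

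| D | σw | Half-width, pooled / stratified | Coverage of pooled 95% CI | Power, pooled / stratified |
|---|---|---|---|---|
| 0 | 14.0 | 6.2 / 6.2 | 95% | 82.1% / 81.9% |
| 5 | 13.8 | 6.2 / 6.1 | 95.3% | 82.3% / 82.9% |
| 10 | 13.1 | 6.2 / 5.8 | 96.3% | 83.4% / 86.5% |
| 15 | 12.0 | 6.2 / 5.3 | 97.7% | 85.1% / 91.7% |

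The power given up is 0.6, 3.1 and 6.6 points at D = 5, 10 and 15. At D = 0 stratifying costs 0.2 points.

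**If 14 is taken as the within-group SD instead,** the stratified half-width is 6.23 throughout, and the pooled one is 6.30 at D = 5, 6.51 at D = 9 and 7.02 at D = 15: too wide by 1%, 5% and 13%.

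**What a pooled mean can hide (illustration only).** A mean gain of 13.5 in 14 children and 0 in 8 adults gives 14 × 13.5/22 = 8.6, close to the planned 9. The pooled test would be significant for improvement in about 81% of such trials with overall SD 14, or about 72% with within-group SD 14.

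**Precision by group at SD 14.** Children: t(13) × 14/√14 = 2.160 × 3.742 = ±8.1. Adults: t(7) × 14/√8 = 2.365 × 4.950 = ±11.7.

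**The case against.** The strongest reply is that the effect is small and on the safe side. A pooled paired test neither biases the estimate nor inflates type I error, and the loss is trivial unless the groups differ by about 10 points, which is more than the whole planned effect of 9. The mechanisms proposed in section 1.5 are stated for SBS generally, not by age. In a 26-subject, open-label exploratory study, a single pooled test is a legitimate choice. All of this stands and limits the point to a modest one.

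It also stands that the argument holds only for the mean at the achieved age mix. Quotas fix who is enrolled; attrition, which section 6.4 allows up to 20%, can shift who is evaluable.

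Two stronger readings are tempting, and neither is supported:
- A reader might infer that children and adults enter under different eligibility rules. Section 3.4.1 splits on age at resection, not current age: "If small bowel resection occurred at 18 years of age or older, subjects must have 200 centimeters or less of residual bowel length" and more than three bowel movements a day, whereas resection before 18 requires at least three months of parenteral nutrition. Every child falls under the second rule, and so does an adult resected in childhood. The recruitment groups and the eligibility split are different variables.
- A reader might infer that the conclusion should be limited to whichever group shows a gain. The groups are too small for that. If both truly gain 9 points (SD 14, 14 + 8), power is 60% in children and 35% in adults. Both would be significant in 0.60 × 0.35 = 21% of trials, and exactly one in 0.60 × 0.65 + 0.40 × 0.35 = 53%. Such a rule would credit a shared effect to one group more often than not.

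**Conclusion.** The point holds in a limited form. The design fixes the age mix and the analysis ignores it, so the pooled standard error carries any child-adult difference in mean change. The consequence is a conservative test: power loss under 1 point at a difference of 5, about 3 at 10 and about 7 at 15, and none if the groups respond alike.

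These sizes assume 14 + 8 evaluable, an overall SD of 14 and a common within-group SD. The size of any difference is unknown. The coverage figures describe a t-interval for the change, which section 6.3.1 does not explicitly plan. The stated power in section 6.4 is not in question.

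The absence of any result by age group is a separate reporting gap. It calls for descriptive estimates, not a subgroup test.

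**What to change.** In section 6.3.1:
- Analyse the paired change in CFA, and likewise CNA and BC, by regressing it on an indicator for the two recruitment age groups (4 to 17.9 and 18 to 75 years), centred at its mean among evaluable subjects. Test the intercept and report it as the mean change with its 95% CI. The intercept equals the pooled mean.
- Where skewness triggers the Wilcoxon fallback, use a version stratified by age group, or keep the planned test as a sensitivity analysis.
- Report each age group's mean change with 95% CI as descriptive only, and state the evaluable age mix to which the pooled estimate applies.

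This is a wording change, and date of birth is already collected. It costs one degree of freedom, about 0.2 points of power if the groups do not differ. The by-group intervals will be wide, about ±8 points in children and ±12 in adults, and the text should say so.
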